8 STATISTICAL CONSIDERATIONS

8.1 STATISTICAL ANALYSIS PLAN

Preliminary data analysis: One-way ANOVA will be used to compare demographic and baseline clinical characteristics across groups. **no missing data expected, SAS, p-value

Aim 1 Analysis: For the between-group analysis of functional connectivity, general linear model multivariate analysis of variance will be used with FC values between pairs of LSBN parcellations as dependent variables and group (DLB, AD, and CN) as a factor variable. Bonferroni post hoc test will be used to correct for multiple comparisons. The primary pairs of interest (see **Table 4**) based on available literature (see background and **Table 2**) will be analyzed first. Other combinations of these seven parcellations will be analyzed secondarily. If additional, unexpected anomalies are present between groups, we will test them in an exploratory fashion to advance this novel field of study.

Aim 2 Analysis: Pearson correlation analyses will be performed between functional connectivity values and neuropsychological test scores to evaluate the relationship between connectivity strengths and the clinical phenotype of DLB. Similar to Aim 1, we will focus on pre-specified pairs of interest, but will explore others if they present themselves in the functional connectivity analysis.

Table 4: Data Variables
Population Descriptors: age, sex, race, ethnicity, education, measures of baseline cognition (e.g. MoCA)
Aim 1: Evaluate the role of rs-fMRI and connectomic analysis as a biomarker of disease in DLB using data from an ADNI-2/3 population of MCI and mild AD subjects and a clinic population of DLB subjects
Group variable: DLB, AD, or CN

Dependent variables: Functional connectivity (FC) scores between pairs of LSBN parcellations
 
 • Primary pairs of interest (see background for justification of these choices): 
 ○ Locus coeruleus v. Basal nucleus of Meynert ○ Locus coeruleus v. Intralaminar nucleus of thalamus ○ Basal nucleus of Meynert v. Intralaminar nucleus of thalamus ○ PH v. FST ○ Substantia nigra v. Caudate nucleus • Exploratory pairs: Other 15 combinations of the pre-specified parcellations, other pairs of parcellations found to be anomalies by Infinitome program
Aim 2: Correlate cross-sectional dysfunction between LSBN parcellations with specific neuropsychological abnormalities in DLB Patients

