06 FEB 2024

Aim 1

Our primary aim was to evaluate the role of rs-fMRI and connectomic analysis as a diagnostic imaging biomarker of disease for LSBN deterioration in DLB by comparing a clinical population of DLB patients with the ADNI 2/3 cohort of CN and AD/CI subjects. Specifically, we compared FC scores of prespecified parcellation pairs between the three groups using a one-way ANOVA. Eight parcellation pairs were chosen as the primary pairs, and twenty-two as the exploratory pairs.

Aim 2

Our secondary aim (aim 2) was to correlate cross-sectional dysfunction between LSBN parcellations with specific neuropsychological abnormalities in DLB patients. To accomplish this, we performed a two-stage analysis. First, we compared cognitive test scores between groups to understand which successfully distinguished between the cohorts. When possible, test scores were normed, i.e., converted to a Z- or T-score adjusted for age, sex, and years of education.

Primary Comparisons/A Priori Hypotheses:

- 1) *ADAS Number Cancellation Targets will be lower in DLB patients*
- 2) *Trails B time will be higher in DLB patients*
- 3) *Clock Drawing Tests will be lower in DLB patients*
- 4) *ADAS construction praxis score will be lower in DLB patients*
- 5) *Category Fluency Animals will be lower in AD patients*
- 6) *RAVLT recognition will be lower in AD patients*

The remaining comparisons were exploratory: Trails A time, RAVLT immediate recall, RAVLT delayed recall, Functional Activities Questionnaire (FAQ), Logical Memory Immediate, and Logical Memory Delayed. Digit Span Forward, Digit Span Backward, and Boston Naming Test were either missing or highly incomplete in ADNI controls; therefore, they were described in the DLB cohort only.

In the second part of the Aim 2 analysis, we correlated test scores with FC scores from the primary parcellation group in Aim 1, within diagnosis (DLB, CN, or AD/CI) and compared these correlations across diagnosis group. As above, we prespecified 4 hypotheses to test and consider the remaining correlations to be exploratory. Because of the high volume of statistical tests performed in the exploratory analysis, we used the Holm correction to adjust the p-values in the exploratory correlations only.

Primary/ A Priori Hypotheses:

- 1) *Caudate R / Substantia Nigra R and the Clock Drawing Test will be differently correlated for DLB patients vs other groups.*

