- 2) *Caudate R/ Substantia Nigra R and the ADAS Number Cancellation Targets will be differently correlated for DLB patients vs other groups.*
- 3) *FST R/PH R and the ADAS construction praxis will be differently correlated for DLB patients vs other groups.*
- 4) *FST R / PH R and the Clock Drawing Test will be differently correlated for DLB patients vs other groups.*

With respect to the exploratory correlations, we used a significance threshold of $p < 0.15$, which is an accepted approach for detecting effects in emerging research areas where it's preferable to err on the side of identifying novel effects versus failing to reject a null hypothesis when it is false (Type II error).

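### Aim 2 asks whether connectivity tracks cognition in DLB patients, but its four a priori correlation hypotheses test only whether DLB differs from other groups

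*Combined protocol and SAP*

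**What the plan says.** The updated SAP words the aim as a question about one group: "Our secondary aim (aim 2) was to correlate cross-sectional dysfunction between LSBN parcellations with specific neuropsychological abnormalities in DLB patients". Protocol section 8.1 plans Pearson correlations for the same purpose, "to evaluate the relationship between connectivity strengths and the clinical phenotype of DLB".

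In the second part of Aim 2, the updated SAP correlates test scores with connectivity scores "within diagnosis (DLB, CN, or AD/CI) and compared these correlations across diagnosis group". It then names four a priori hypotheses. The first is "Caudate R / Substantia Nigra R and the Clock Drawing Test will be differently correlated for DLB patients vs other groups", the second "Caudate R/ Substantia Nigra R and the ADAS Number Cancellation Targets will be differently correlated for DLB patients vs other groups" and the fourth "FST R / PH R and the Clock Drawing Test will be differently correlated for DLB patients vs other groups". The third has the same form, for FST/PH and construction praxis. None gives a direction, and none says that the DLB correlation differs from zero. All other correlations are exploratory, with Holm adjustment and a threshold of 0.15.

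Aim 2 also lists six primary comparisons in its first part. These compare test scores between groups and involve no correlation with connectivity.

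**The concern.** The aim concerns an association within DLB, while the hypotheses concern a contrast between DLB and other diagnoses. These are different quantities, and either can be zero when the other is not. If DLB shows no association but a comparator does, a hypothesis of different correlation is true. If every group shares a strong association, that hypothesis is false although the answer to the aim is yes.

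The within-DLB correlations are computed, but the plan does not say what finding in them would count as an answer. A significant contrast could then be presented as a brain-behaviour link in DLB without the DLB estimate supporting it. A real link that is not specific to DLB could be presented as a null result.

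**Working it through.** **Plan's own figure.** The documents give no power or precision figure for Aim 2. The nearest is the 81% in section 8.2 for Aim 1 post-hoc t-tests (19 v 38, difference 0.05, SD 0.05, two-sided alpha 0.01). A noncentral t calculation gives 80.9%, so it reproduces, but it does not bear on this point.

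**Inputs from the documents.** 19 DLB, 38 AD and 38 CN (section 8.2); Pearson correlation (section 8.1).

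**Assumptions.** Bivariate normal data, Fisher z for comparing correlations, two-sided alpha 0.05, and the true correlations shown below. The SAP states none of these.

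**Formulas.** Let z = atanh(r), so z(0.6) = 0.693.
- Within DLB: SE = 1/√(19−3) = 0.25. At r = 0.6, 0.693/0.25 = 2.77 and power ≈ Φ(2.77 − 1.96) = 0.79. Simulation with the exact t-test on r gives about 0.82.
- DLB v one comparator: SE = √(1/16 + 1/35) = 0.302. For 0 v 0.6, 0.693/0.302 = 2.30 and power ≈ Φ(2.30 − 1.96) = 0.63 (about 0.65 by simulation).
- DLB v 76 pooled: SE = √(1/16 + 1/73) = 0.276. For 0 v 0.6, 0.693/0.276 = 2.51 and power ≈ Φ(2.51 − 1.96) = 0.71 (about 0.72 by simulation).
- Three-group test: chi-square on 2 df of the weighted z values about their mean.

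**Rejection rates (%), by simulation except where marked.**

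| True r: DLB / AD / CN | Within DLB | DLB v AD | DLB v CN | DLB v the two combined | Three-group test | Both contrasts required |
|---|---|---|---|---|---|---|
| 0.6 / 0.6 / 0.6 | 82 | 5 | 5 | 5 | 5 | below 5 |
| 0.6 / 0.6 / 0 | 82 | 5 | 66 | 25–30 | 83 | 3 |
| 0 / 0.6 / 0.6 | 5 | 65 | 65 | 72 | 60* | 52 |
| 0 / 0.6 / 0 | 5 | 65 | 5 | 21 | 83 | 3 |

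*Noncentral chi-square approximation. In the second row, 25–30 depends on whether the comparators' z values are averaged or their data pooled. In rows two and four, the AD–CN difference alone can trigger the three-group test.

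**Sensitivity to alpha.** At 0.0125 (Bonferroni for four hypotheses), Fisher z approximations give the following. With zero in DLB and 0.5 to 0.6 in both comparators, the single-contrast, pooled and three-group tests reject 22% to 51% of the time. With 0.6 everywhere, they reject 1.25%, against 61% within DLB.

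**A link confined to DLB** (0.6 in DLB, 0 in both comparators, alpha 0.05). A single contrast has about 66% power, against about 82% within DLB.

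**Precision.** An observed r of 0.6 in 19 patients has z limits 0.693 ± 1.96 × 0.25 = 0.203 to 1.183, so a 95% CI of about 0.20 to 0.83.

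**The case against.** The strongest defence is that comparing correlations across diagnoses is a sensible question for a study seeking a diagnostic biomarker. A correlation common to all groups would say nothing specific to DLB. That stands, and it is why the contrasts should be kept. It does not make them an answer to the aim as worded.

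A reader might infer that the within-DLB analysis has been dropped. The documents do not support that: the correlations are computed within each diagnosis, and nothing says they would be withheld. What is missing is a hypothesis or rule that uses them.

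A reader might also infer that a DLB link shared with AD would be reported as negative. The documents do not support that either. The hypotheses refer to other groups, which include CN, and the SAP does not define the contrast. With 0.6 in DLB and AD and 0 in CN, rejection runs from 3% to 83% depending on the rule. Near-certain failure requires that CN share the correlation too, or that only the AD contrast counts, or that DLB must differ from both groups. For the same reason, no single percentage can be called the performance of the planned test.

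Finally, the updated SAP is written in the past tense. If the analyses have been run, promoting a new directional test now would be post hoc. This limits the remedy. It does not block it, because section 8.1 already planned the correlation analysis for the DLB phenotype.

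**Conclusion.** The mismatch holds on the wording alone: no a priori hypothesis in Aim 2 tests the association that the aim names. At these sample sizes it matters. With a correlation of 0.6 in all groups, the difference is detected about 5% of the time and the DLB association about 82%. With zero in DLB and 0.6 in both comparators, the difference is significant about 52% to 72% of the time across the rules tabulated. If only AD carries the correlation, the range is 3% to 83%.

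These figures rest on Fisher z, two-sided 0.05, full recruitment at 19/38/38 and assumed correlations. The width of the ranges comes from the SAP naming no comparison test, pooling rule or alpha. Aim 2 is secondary, so the consequence is a misleading secondary conclusion and does not touch Aim 1.

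**What to change.** For each of the four pair-test combinations, report the within-DLB Pearson correlation with its 95% CI and a two-sided test against zero, at a stated alpha, as the result that answers Aim 2. Keep the DLB v AD/CI and DLB v CN differences in correlation as the specificity analysis. Report them as two separate contrasts and name the test used. Claim a DLB-specific link only when the DLB correlation and the differences both support it.

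If the analyses have already been run, disclose that timing and do not add an expected sign afterwards.

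The cost is SAP and reporting text plus confidence intervals for correlations already computed; no new patients or data are needed. The downside is that the within-DLB result alone does not speak to specificity, and its intervals will be wide with 19 patients.
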